2.1 Study Objectives

Table 1: Study Objectives and Endpoints

Objectives	Endpoints
Primary	
To evaluate the confirmed complete and partial response (CR + PR) rate of mirdametinib using volumetric magnetic resonance imaging (MRI) analysis, as assessed by a blinded independent central review (BICR), in participants with an inoperable NF1 associated PN that is causing significant morbidity.	Objective response rate at the end of the Treatment Phase (defined as PN decrease ≥ 20% compared to baseline in consecutive scans 2-6 months apart) using centrally read MRI volumetric analysis.

Document: S:\Q_146\Q_03974\MEK-NF-201\Prog_Stat\Documentation\SAP\MEK-NF-201 SAP v1.0.0.docx

Secondary	
-	Cofety and points will include incidence of
To evaluate the safety and tolerability of mirdametinib in participants with NF1 and symptomatic inoperable PN as measured by the incidence of adverse events (AEs)	Safety endpoints will include incidence of treatment-emergent adverse events, changes in laboratory parameters, vital signs, physical examination findings, and electrocardiograms (ECGs); Incidence of treatment-emergent adverse events will also be assessed by dose formulation.
	Tolerability will be assessed according to toxicities graded by National Cancer Institute (NCI) Common Terminology Criteria for Adverse Events (CTCAE) Version (v) 5.0;
To determine the duration of response (DoR)	Duration of response for participants whose best overall confirmed response is complete response (CR) or partial response (PR) using centrally read MRI volumetric analysis
To evaluate the effect of mirdametinib on quality of life as measured by patient-reported outcomes (PROs)	Change from baseline in quality of life (QoL) assessed by the age-specific Pediatric Quality of Life Inventory
	The number of participants with a meaningful score change as derived from the anchor analysis.
To evaluate the effect of mirdametinib on pain as measured by PROs	Change from baseline in pain assessed using the Numeric Rating Scale-11 and Pain Interference Index (PII)
	The number of participants with a meaningful score change as derived from the anchor analysis.
Exploratory	
To evaluate the effect of mirdametinib on physical functioning as measured by PROs	Change from baseline in physical function status (Patient-Reported Outcomes Measurement Information System [PROMIS] - Physical Function/Mobility/Upper Extremity Scale) in the Treatment Phase

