2.2 Study Design

MEK-NF-201 is a multi-center, open-label, single-arm, longitudinal, uncontrolled, Phase 2b study to evaluate the efficacy, safety, and tolerability of mirdametinib in participants ≥ 2 years of age with an inoperable NF1-associated PN that is causing significant morbidity.

This study will consist of two phases: the Treatment Phase and the optional Long-Term Follow-Up (LTFU) Phase. Approximately 100 participants will be enrolled and stratified by age (approximately 50 participants 2 to 17 years of age and 50 participants ≥ 18 years of age). The first five participants enrolled in the pediatric cohort must be 9 to 17 years of age at the time of signing informed consent/assent. After the first 5 participants have enrolled in the pediatric cohort, enrollment into this cohort will be paused, and only after Data Monitoring Committee (DMC) evaluation of at least 2 cycles of cumulative safety data for these 5 participants will the pediatric cohort be re-opened and potentially expanded down to 2 years of age. Note the adult cohort will not be affected by this special procedure; participants ≥ 18 years of age will be enrolled continuously from the outset.

Document: S:\Q_146\Q_03974\MEK-NF-201\Prog_Stat\Documentation\SAP\MEK-NF-201 SAP v1.0.0.docx

Participants will be screened for up to 45 days prior to the first dose of study treatment (mirdametinib) and eligibility will be based on the inclusion and exclusion criteria listed in Sections 5.1 and 5.2 of the protocol, respectively. Study treatment will then be administered orally at a dose of 2 mg/m² BID with a maximum dose of 4 mg BID. Dosing in the Treatment Phase will be on a 28-day cycle with a 3 week on/1 week off schedule for up to 24 Cycles. Eligible participants will take their first dose of study treatment following all pre-dose assessments on Cycle 1 Day 1. All participants will remain in the Treatment Phase of the study until radiographic disease progression (confirmed by central review), they discontinue study treatment for any other reason, the study is stopped by the sponsor for any reason, or the participant has completed the study through Cycle 24.

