Document: S:\Q_146\Q_03974\MEK-NF-201\Prog_Stat\Documentation\SAP\MEK-NF-201 SAP v1.0.0.docx
Author:

Statistical Analysis Plan SpringWorks Therapeutics Protocol Number: MEK-NF-201

In addition to the anchor-based estimates described above, the number and percentage of participants with a within-patient meaningful score change estimates are defined below and will be considered as a supportive analysis. For PedsQL Scale Scores, the meaningful score difference will be defined separately for adult, pediatric self-report, and pediatric parent proxy data. In each case, it will be defined as 0.5*SD, where SD is calculated from the baseline Scale Score data. This is in-line with the difference used on the selumetinib SPRINT study (Gross, 2018) and serves as the lower bound for minimally detectable change (Norman, 2003).

The number and percentage of participants with a change representing a clinically meaningful improvement (alongside associated 95% Clopper-Pearson Cls) will be presented for both thresholds.

In addition, within each age cohort, the proportion of participants reaching the anchor-based and distribution threshold will be analyzed in the subgroup of participants who have a confirmed objective response status versus the subgroup of those who do not. This is to further characterize the relationship between PRO improvement and the clinical endpoint of tumor response. The proportion of participants reaching the anchor-based (and distribution) thresholds will be summarized with 95% Clopper-Pearson Cls by confirmed objective response status, and the differences in the proportions of participants reaching the anchor-based/distribution thresholds between responders and non-responders will be tested using a Chi-Square test at a 5% significance level.

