6.11.2.3 Change from Baseline in pain (assessed using the NRS-11 and PII)

6.11.2.3.1 NRS-11

All NRS-11 records will be listed by participant and visit.

The number and percentage of participants in each of the result categories (Appendix 1.3) at baseline will be summarized. Absolute values and change from baseline will be summarized overall and by confirmed objective response status (as defined with confirmed response rate in Section 4.1.1 using adjudicated values where appropriate), by visit and age cohort, the summaries presented will be number and percentage of participants with a non-missing score, mean, SD, median, minimum, and maximum values.

For NRS-11, a within-patient meaningful score change, or meaningful score difference (FDA, 2023), will be derived by anchor-based analysis of the study's data as described in the meaningful change threshold analysis plan (Version 1.0, dated 12Sep2023). The primary focus of this will be on if such a relevant difference exists at Cycle 13.

Additionally the number and percentage of participants with a change representing a clinically meaningful improvement (alongside associated Clopper-Pearson confidence intervals) will be presented using change from baseline of ≤ -1 (This cut point has previously been researched and assessed as a meaningful change in pediatric populations (Hirschfeld, 2014)), representing a clinically meaningful improvement, will be presented, as well as change from baseline greater than the within-patient meaningful change threshold (i.e., derived by anchor-based analysis of the study's data in accordance with the MCT SAP; see Section 5.8 above) will be presented.

In addition, within each age cohort, the proportion of participants reaching the anchor-based and distribution threshold will be analyzed in the subgroup of participants who have a confirmed objective response status versus the subgroup of those who do not. This is to further characterize the relationship between PRO improvement and the clinical endpoint of tumor response. The proportion of participants reaching the anchor-based (and distribution) thresholds will be summarized with 95% Clopper-Pearson Cls by confirmed objective response status, and the differences in the proportions of participants reaching the anchor-based/distribution thresholds between responders and non-responders will be tested using a Chi-Square test at a 5% significance level.

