6.11.2.3.2 PII

All PII records will be listed by participant, visit, and questionnaire type (self-report/parent proxy).

Absolute values and change from baseline will be summarized, overall and by confirmed objective response status (as defined with confirmed response rate in Section 4.1.1 using adjudicated values where appropriate), by visit and age cohort with self-report and parent proxy scores presented separately. The summaries presented will be number and percentage of participants with a non-missing score, mean, SD, median, minimum, and maximum values.

For PII a within-patient meaningful score change, or meaningful score difference (FDA, 2023), will be derived by anchor-based analysis of the trial's data, as described in the meaningful change threshold analysis plan (Version 1.0, dated 12Sep2023). The primary focus of this will be on if such a relevant difference exists at cycle 13.

Additionally, the number and percentage of participants with a change representing a clinically meaningful improvement (alongside associated 95% Clopper-Pearson confidence intervals) will be presented using the change from baseline of <-0.5*SD (using SD from baseline)(This is in-line with the difference used for analyzing PII on the selumetinib SPRINT study (Gross, 2018).) as well as change from baseline greater than the within-patient meaningful change threshold (i.e., derived by anchor-based analysis of the trial's data in accordance with the MCT SAP; see Section 5.8 above) in separate analyses.

In addition, within each age cohort, the proportion of participants reaching the anchor-based and distribution threshold will be analyzed in the subgroup of participants who have a confirmed objective response status versus the subgroup of those who do not. This is to further characterize the relationship between PRO improvement and the clinical endpoint of tumor response. The proportion of participants reaching the anchor-based (and distribution) thresholds will be summarized with 95% Clopper-Pearson Cls by confirmed objective response status, and the differences in the proportions of participants reaching the anchor-based/distribution thresholds between responders and non-responders will be tested using a Chi-Square test at a 5% significance level.

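### The PedsQL, NRS-11 and PII meaningful-change rates count improvement only, with no matching worsening rate or reference rate, so the improvement percentage cannot be read on its own

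*SAP*

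**What the plan says.** SAP 2.2 describes a "multi-center, open-label, single-arm, longitudinal, uncontrolled, Phase 2b study". For both quality of life and pain, SAP Table 1 (2.1) lists change from baseline first and then "The number of participants with a meaningful score change as derived from the anchor analysis". That second line gives no direction.

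The analysis sections do give one:

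- **PedsQL (6.11.2.2):** "The number and percentage of participants with a change representing a clinically meaningful improvement", for both the anchor-based and the distribution threshold. On the latter: "In each case, it will be defined as 0.5*SD, where SD is calculated from the baseline Scale Score data". The half-SD version "will be considered as a supportive analysis".
- **NRS-11 (6.11.2.3.1):** "Additionally the number and percentage of participants with a change representing a clinically meaningful improvement" "will be presented using change from baseline of ≤ -1", and also at the anchor-based threshold. The visit score is a seven-day mean of daily worst pain on a 0 to 10 scale (4.1.2.2.2).
- **PII (6.11.2.3.2):** "Additionally, the number and percentage of participants with a change representing a clinically meaningful improvement", defined as a fall of more than half a baseline SD, and also at the anchor-based threshold.

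All are reported with Clopper-Pearson intervals. Cycle 13 is the timepoint of interest (5.8). The anchor-based value is left to a separate threshold plan. Historical controls are planned for TTP and PFS only (Table 1).

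**The concern.** A proportion improving by a threshold has a natural zero only if nobody crosses the threshold by chance. With a threshold of half a baseline SD, which the SAP itself places at the lower limit of what can be detected, ordinary within-person variation carries many participants across it in each direction. A controlled trial handles this by subtracting the control rate. This trial has no control arm, and the SAP supplies neither a no-effect rate nor a count of those who worsen by the same amount.

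At stake is how the table is read. An improvement rate of about a quarter, with an interval well clear of zero, looks like benefit. The table does not show whether a similar share got worse. The protocol calls the study potentially registrational (9.2), so these secondary tables may be read closely.

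**Working it through.** **Reproducing the plan.** The documents give no expected, null or reference rate for the PRO proportions, so there is none to reproduce. As a check on the interval method, the exact lower bounds for the SAP's own tumor-response examples (2.3) are 28.2% for 21/50 and 49.2% for 32/50. These agree with the stated exclusion of 28% and 49%.

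**Inputs from the documents:** the half-SD rule for PedsQL and PII; a fall of at least 1 point for NRS-11; about 50 participants per cohort (fewer are eligible for self-report among young children, SAP Table 14).

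**Assumptions, because the documents are silent:** baseline and Cycle 13 scores are bivariate normal with equal means and SDs and test-retest correlation *r*; for NRS-11, also the SD and the share of participants at the scale floor.

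**Half-SD rule, no true change.** SD of change = SD × √(2(1 − r)). P(improved) = 1 − Φ(0.5 / √(2(1 − r))). P(worsened) is the same by symmetry.

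| r | SD of change (baseline SDs) | 0.5 ÷ SD of change | Improved = worsened | Improved of 50 | Exact 95% CI |
|---|---|---|---|---|---|
| 0.5 | 1.000 | 0.500 | 30.9% | 15 | 17.9% to 44.6% |
| 0.6 | 0.894 | 0.559 | 28.8% | 14 | 16.2% to 42.5% |
| 0.7 | 0.775 | 0.645 | 25.9% | 13 | 14.6% to 40.3% |
| 0.8 | 0.632 | 0.791 | 21.5% | 11 | 11.5% to 36.0% |
| 0.9 | 0.447 | 1.118 | 13.2% | 7 | 5.8% to 26.7% |

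Simulating PedsQL clipped to 0–100 (assumed mean 65 or 75, SD 18) changes these figures by less than one percentage point.

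**NRS-11, no true change.** P(change ≤ −1) = 1 − Φ(1 / (SD × √(2(1 − r)))).

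| SD | r = 0.5 | r = 0.7 | r = 0.9 |
|---|---|---|---|
| 1.5 | 25.2% | 19.5% | 6.8% |
| 2.0 | 30.9% | 25.9% | 13.2% |
| 2.5 | 34.5% | 30.3% | 18.6% |
| 3.0 | 36.9% | 33.3% | 22.8% |

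Clipped to 0–10 with latent SD 2.5 and about a third of participants at zero, the rate runs from 24.8% (r = 0.5) to 11.6% (r = 0.9). Floor cases are plausible because pain is only one of several qualifying morbidities (protocol 5.1, criterion 3). The range is too wide to quote one number.

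**Anchor-based threshold.** With no stated value, no rate can be computed. Purely as illustration, over r = 0.9 to 0.5 a threshold of 0.75 SD gives 5% to 23%, and one of 1.0 SD gives 1% to 16%.

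**What a paired row would show.** With *b* improved and *c* worsened of *n*, the net is (b − c)/n and its variance is [(b + c) − (b − c)²/n]/n². For b = c = 13 and n = 50, the net is 0, the variance is 26/2500 = 0.0104 and the SE is 0.102. The Wald 95% CI is 0 ± 1.96 × 0.102, about −20 to +20 percentage points. The improvement row alone, from the same data, reads 26% (14.6% to 40.3%).

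**The case against.** The strongest reply is that the plan already contains signed analyses. SAP 5.5.1.1 makes a mixed model of change from baseline the main PedsQL analysis, and 6.11.2.3.1 and 6.11.2.3.2 fit the same model for NRS-11 and PII, with means, intervals and p-values by visit. Mean change sets worsening against improvement and is centered on zero with no true change. Waterfall plots at Cycles 5 and 13 show every participant's direction, and PGIC counts include the worse categories (6.11.3.4). The proportions are compared between confirmed tumor responders and non-responders by chi-square. This stands: a reader might infer that nothing in the plan weighs worsening against improvement, and that is not so.

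Two other stronger readings also fail. One is that a fifth to a third would be called improved on all three instruments. The figure belongs to the half-SD rule at assumed correlations. It does not carry over to NRS-11 or to the anchor-based threshold that Table 1 names. The other is that the plan risks a false claim because the interval will exclude zero. The SAP tests none of these rates against zero and sets no success cut-off for them.

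It is also fair to say that a worsening display may sit in the separate threshold plan, which is not among these documents, and that a net rate does not remove regression to the mean or open-label expectation.

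What the reply does not reach is the percentage itself. The model speaks to the mean, the chi-square to association with tumor response, and the plots give no worsening count or interval. None tells a reader how much of an improvement rate would arise with no effect.

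**Conclusion.** The point holds as a gap in reporting. In this SAP the three meaningful-change proportions run in one direction only, although the Table 1 endpoint is undirected, and they have no worsening counterpart and no reference rate in an uncontrolled trial. For the half-SD rule (supportive for PedsQL; also used for PII), about 31% to 21% would be labelled improved with no true change at r = 0.5 to 0.8, and about 13% at r = 0.9. An equal share would worsen. These figures rest on normal scores, a stable mean and SD, and correlations that the documents do not give. No single figure is available for NRS-11, and none can be computed for the anchor-based threshold. The primary analysis is untouched, and the mixed models remain the evidence on mean PRO effect.

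**What to change.** In SAP 6.11.2.2, 6.11.2.3.1 and 6.11.2.3.2, at Cycle 13:

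1. Beside each improvement rate, tabulate the percentage worsening by the same magnitude. For the anchor-based threshold, use the deterioration threshold if the separate threshold plan derives one, since symmetry cannot be assumed.
2. Add improved minus worsened with a paired 95% CI as a supporting row. Keep the mixed model as the main analysis.
3. State that the improvement rate alone is not evidence of drug effect, and that the net rate removes symmetric noise only, not regression to the mean or open-label expectation.

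The cost is two rows and one paired interval per table, from data already collected, with no change to conduct. The headline figure will be less flattering. NRS-11 and PII participants who start at the scale floor can only worsen, so they cannot contribute to a benefit and the net is conservative for them; the tables should say how many there are.

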4.1.1 Primary Efficacy Measure

The primary efficacy endpoint of interest is the confirmed ORR by the end of Treatment Phase (i.e., Cycle 24). The confirmed ORR is defined as the proportion of participants who have a confirmed ≥ 20% reduction in target tumor volume as compared to baseline as assessed by a BICR, and the response needs to be confirmed by BICR in a consecutive tumor assessment within 2 − 6 months.

To determine the level of target tumor response (complete response [CR], partial response [PR], stable disease [SD], or progressive disease [PD]) which are described below, post-baseline measurement scans are compared to the target PN volume in the pre-treatment MRI scan using volumetric data analysis:

- CR: A complete resolution of the target PN
- PR: A ≥ 20% reduction in the volume of the target PN lesion compared to baseline
- SD: Between a < 20% increase and < 20% decrease in the volume of the target PN lesion compared to baseline
- PD: A ≥ 20% increase in the volume of the target PN compared to baseline. (Radiographic disease progression)

The best overall confirmed response (CR, PR, SD, PD, NE - where SD/PD/NE only require a singular response to be deemed confirmed at that level) will be summarized. For participants that remain on treatment after PD, only the best response up to PD will be considered. For participants who only have one response measurement, and this is a CR or PR (and therefore unconfirmed), their best overall response status will be set to "Missing".

All tumor volume measurements will be independently calculated by two BICR readers. In the case that the two measurements represent different tumor response statuses, as defined above, an independent adjudicator will make the final decision on which response category is recorded at that visit. The primary endpoint analysis will be performed using the adjudicator-selected reader for those visits where the two BICR readers did not agree.

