Tumor volume (mL) will be assessed using MRI scans that will be taken at screening, then every 4 cycles at Cycles 5, 9, 13, 17, 21, 24, and ET for the Treatment Phase, and Cycle 28 and every 4 cycles after that, up to and including end of treatment (EOT), for the LTFU Phase, if applicable. Only tumor assessments during the Treatment Phase and prior to the first treatment start date in the long-term follow up will be considered for the determination of confirmed response. Unscheduled visits will be mapped to a visit window based on the criteria in Section 5.6.

The FAS will be used to calculate the confirmed ORR. Participants who do not have a post-baseline MRI assessment or do not achieve a confirmed response will be categorized as non-responders, and their best overall response will be deemed as "Missing".

Document: S:\Q_146\Q_03974\MEK-NF-201\Prog_Stat\Documentation\SAP\MEK-NF-201 SAP v1.0.0.docx

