5.8 PRO Analysis

All PROs analyzed in this study will be assessed using the mean change from baseline as well as by participants achieving of a meaningful score difference at the Cycle 13 visit.

Document: S:\Q_146\Q_03974\MEK-NF-201\Prog_Stat\Documentation\SAP\MEK-NF-201 SAP v1.0.0.docx

Author:

Cycle 13 has been selected as the timepoint that will best allow the treatment effect to be captured in PRO scores. It is projected that a strong majority of participants who present a response will do so at or before Cycle 13, with the median time of response expected to be Cycle 5 to Cycle 9, so any associated pain or QoL improvements should be captured at the Cycle 13 visit. Choosing a later cycle would capture few additional responses and may be susceptible to increased amounts of missing data.

An addendum meaningful change threshold (MCT) SAP will provide detailed descriptions of the statistical methods, data derivations, and data displays for the meaningful change analyses of the clinical outcome assessment (COA) data collected in the MEK-NF-201 study. This addendum (PRO Addendum) for the meaningful change threshold analysis plan (MCTAP) is based on the MEK-NF-201 Protocol Amendment 4 dated 17 May 2022.

Statistical Analyses

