6.11.2 Secondary Efficacy Analyses

6.11.2.1 Duration of response for participants whose best response is CR or PR using centrally read MRI volumetric analysis

DoR will be analyzed using Kaplan-Meier (KM) methods, with the median, lower, and upper quartile estimates of DoR and the corresponding 95% Cls (using the Brookmeyer and Crowley method). The number of participants with events (i.e., radiographic disease progression or death) or who are censored, as well as reason for censoring, will be presented separately by age cohort. "NE" will be presented where estimates of such were not estimable. Additionally, KM plots will be presented separately for each age cohort and will contain the number of participants at risk and the event rate. In addition, KM estimates with 95% Cls (using the log-log transformation) will also be presented at key timepoints such as 8, 12, 16, 20, and 24 months.

Censoring rules and the definition of confirmed response are laid out in Section 4.1.2.1.

The sensitivity analyses using REiNS criteria as outlined in Section 4.1.2.1.1 will also be summarized using the same method as described above.

In addition, a swimmer plot will be used to present duration of treatment (in days) where radiographic progression, first onset and confirmation of confirmed response, whether still on study at cutoff and death are displayed, split by cohort.

6.11.2.2 Change from Baseline in quality of life assessed by the age specific Pediatric Quality of Life Inventory

All PedsQL records will be listed by participant, visit and questionnaire type (self-report/parent proxy).

Actual values and change from baseline for each score listed in Section 4.1.2.2.1 will be summarized for each age cohort by visit, for participants overall and by confirmed objective response status (as defined with confirmed response rate in Section 4.1.1 using adjudicated values where appropriate) with self-report and parent proxy scores presented separately. The summaries presented will be number and percentage of participants with a non-missing score, mean, SD, median, minimum, and maximum values.

For PedsQL, a within-patient meaningful score change, or meaningful score difference (FDA, 2023), will be derived by anchor-based analysis of the study's data, as described in the meaningful change threshold analysis plan (Version 1.0, dated 12Sep2023). The primary focus of this will be on if a relevant difference exists at Cycle 13.

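### The Cycle 13 comparison of PRO improvement by tumor response uses response status from the whole Treatment Phase, so first responses at Cycle 17 or 21 count as already present

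*SAP*

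**What the plan says.** **PRO time point.** SAP 5.8 assesses PROs by mean change from baseline and by "participants achieving of a meaningful score difference at the Cycle 13 visit". SAP 7.1 repeats that Cycle 13 is the time of interest for PRO analysis. SAP 5.8 gives the reason: most responders are projected to respond by Cycle 13, with a median between Cycles 5 and 9, so any associated gain in pain or quality of life should be visible by then.

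**Grouping variable.** For PedsQL, NRS-11 and PII, the SAP compares the proportion reaching the anchor-based and distribution thresholds in "the subgroup of participants who have a confirmed objective response status versus the subgroup of those who do not", with a chi-square test at the 5% level. The status is "as defined with confirmed response rate in Section 4.1.1 using adjudicated values where appropriate". SAP 4.1.1 defines that endpoint as "the confirmed ORR by the end of Treatment Phase (i.e., Cycle 24" visit), and adds that "the response needs to be confirmed by BICR in a consecutive tumor assessment", 2 to 6 months apart. On eligible scans it says: "Only tumor assessments during the Treatment Phase and prior to the first treatment start date in the long-term follow up will be considered". Scans are taken at screening, "then every 4 cycles at Cycles 5, 9, 13, 17, 21, 24, and ET for the Treatment Phase".

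The chi-square paragraphs do not themselves name Cycle 13. The time point comes from SAP 5.8 and 7.1 and from the statements in 6.11.2.2 and 6.11.2.3 that the threshold analysis focuses on Cycle 13. The same status also colors the waterfall plots at Cycles 5 and 13. The sections on these analyses contain no landmark at Cycle 13, no time-dependent status and no sensitivity analysis by timing of response.

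**The concern.** The outcome is measured at one time and the grouping variable is settled up to 11 cycles later. SAP 5.8 chose Cycle 13 on the argument that PRO gains associated with response should have appeared by then, which presumes that the response has already occurred. For participants who first respond after Cycle 13, that is not so.

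At stake is how one supportive analysis is read. A reader will take the table as PRO improvement in participants whose tumor has, or has not, shrunk by 20%. Some of those in the responder row had not reached that criterion when they completed the questionnaire, and the table does not show how many.

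**Working it through.** **1. Which participants are affected.** SAP Table 12 gives the scan days: Cycle 13 = 351, Cycle 17 = 463, Cycle 21 = 575, Cycle 24 = 665. These follow from (cycle − 1) × 28 + 15, with day 21 in place of day 15 for Cycle 24.

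- Cycle 13 to 17: 463 − 351 = 112 days (3.7 months)
- Cycle 17 to 21: 575 − 463 = 112 days (3.7 months)
- Cycle 21 to 24: 665 − 575 = 90 days (3.0 months)

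All three gaps lie within the 2 to 6 month confirmation window. On scheduled scans:

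| First qualifying scan | Confirmed at | Status in the Cycle 13 test | Criterion met relative to Cycle 13 PRO |
|---|---|---|---|
| Cycle 13 | Cycle 17 | responder | same visit |
| Cycle 17 | Cycle 21 | responder | 112 days later |
| Cycle 21 | Cycle 24 | responder | 224 days later |
| Cycle 24 | no eligible scan left | non-responder | not applicable |

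The mismatch therefore concerns first responses at Cycles 17 and 21, plus any on unscheduled or early-termination scans after Cycle 13.

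**2. How many.** The documents give no count and no power figure for this test. The planning cases in SAP 2.3 are 21 responders of 50 adults and 32 of 50 pediatric participants. Their Clopper-Pearson lower limits reproduce at 28.19% and 49.19%, matching the SAP's statements that 28% and 49% are excluded.

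To get a range, assume an exponential time to first response truncated at day 575: F(t) = (1 − e^(−λt)) / (1 − e^(−575λ)), with λ set so that F(median) = 0.5. The late share is 1 − F(351).

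| Assumed median (SAP 5.8 range) | Late share | Of 21 adults | Of 32 pediatric |
|---|---|---|---|
| Cycle 5 (day 127) | 12% | 2.6 | 3.9 |
| Midway (day 183) | 22% | 4.6 | 7.0 |
| Cycle 9 (day 239) | 31% | 6.5 | 9.9 |

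The exponential shape is an assumption, not something in the SAP.

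**3. What it does to the comparison.** Assume 20 early responders with a 60% improvement rate at Cycle 13, 20 non-responders with 25%, and 5 late responders with rate r.

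- Cycle 24 split: 25 responders with rate (20 × 0.60 + 5r)/25, against 20 non-responders with 0.25.
- Cycle 13 split: 20 responders with 0.60, against 25 others with rate (20 × 0.25 + 5r)/25.

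Power is by exact enumeration of the binomial outcomes with the uncorrected chi-square test at 5%.

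| r | Cycle 24 split: rates, difference, power | Cycle 13 split: rates, difference, power |
|---|---|---|
| 25% | 53% v 25%, 28 points, 48% | 60% v 25%, 35 points, 67% |
| 42.5% | 56.5% v 25%, 31.5 points, 58% | 60% v 28.5%, 31.5 points, 57% |
| 60% | 60% v 25%, 35 points, 67% | 60% v 32%, 28 points, 46% |

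With 23 early and 2 late responders instead, the same calculation gives 60% v 68%, 63% v 63% and 67% v 58%. The gap narrows when late responses are rare, and its sign still depends on r.

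**The case against.** The SAP's stated aim is to relate PRO improvement to the clinical endpoint of tumor response, and that endpoint is confirmed response over the Treatment Phase. On this reading the planned split answers the question asked, and a Cycle 13 split answers a different one. That is fair as far as it goes: the planned split is not invalid and should stay. It does not meet the point that SAP 5.8 justifies Cycle 13 by assuming that response has already happened.

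The SAP also shows awareness of timing. SAP 5.8 projects few additional responses after Cycle 13, the swimmer plot shows onset and confirmation of response, and time to response is summarized in 6.11.3.8. This limits the likely size, but SAP 5.8 gives no number, and none of these displays links timing to the PRO thresholds. The separate meaningful change analysis plan, which is not among the documents, may address it; that cannot be judged here.

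Three stronger readings are tempting and are not supported:

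- *The planned split dilutes the association.* This holds only if late responders resemble non-responders at Cycle 13. Tumor volume is continuous, so someone who crosses 20% at Cycle 17 may already have shrinkage at Cycle 13. Protocol 4.2 also notes symptom improvement without a corresponding large decrease in tumor size.
- *Participants who feel better stay on study longer and so get more chances to be confirmed.* Late responder status does require staying for two further qualifying scans, but nothing in the documents ties retention to PRO benefit.
- *Any response up to Cycle 24 is affected.* A first response at Cycle 24 cannot be confirmed on scheduled Treatment Phase scans.

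**Conclusion.** The mismatch in timing follows directly from SAP 4.1.1, 5.8, 6.11.2.2 and 6.11.2.3. Participants with a first confirmed response at Cycle 17 or 21 are counted as responders for a PRO taken 112 or 224 days earlier. The SAP projects them to be a minority, and their number cannot be derived from the documents.

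No direction of bias can be asserted. In the assumed example, changing only the late responders' Cycle 13 rate from 25% to 60% turns a 19-point power deficit for the planned split (67 − 48) into a 21-point advantage (67 − 46). The case for change is therefore one of interpretation: with both splits shown, a reader can see which situation holds, and with the Cycle 24 split alone they cannot. This is a low-cost improvement to a supportive analysis. The primary endpoint, the overall PRO change and the choice of the chi-square test are not in question.

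**What to change.** For the Cycle 13 threshold tables, the Cycle 13 waterfall plots and the chi-square test, for PedsQL, NRS-11 and PII, add a split by response whose first qualifying scan was at or before the Cycle 13 scan and was subsequently confirmed. Show it beside the existing split, and label the existing one *confirmed response at any time in the Treatment Phase*. The same label would serve the Cycle 5 waterfall plots, where the gap in time is wider.

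The cost is one derived flag. The date of the first response that was later confirmed is already needed for time to response (SAP 6.11.3.8), so no new data are required. There are two downsides to state in the SAP. Late responders move to the non-responder group in the Cycle 13 split, which lowers the contrast if they already feel better. And a first response at Cycle 13 still relies on the Cycle 17 scan for confirmation, so the flag is aligned with when the criterion was met, not with what was known at Cycle 13.
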